8.3.1 Investigator reporting: notifying the study sponsor

The following describes events that must be reported to the study sponsor in an expedited fashion.

Initial Report: within 24 hours:

The following events must be reported to the study sponsor by telephone within 24 hours of awareness of the event:

- Unanticipated problems related to study participation,
- Serious adverse events, regardless of whether they are unexpected.

Additionally, an FDA Form 3500A must be completed by the investigator and faxed to the study sponsor within 24 hours. The investigator shall maintain a copy of the MEDWATCH Form on file at the study site.

Follow-up report: within 48 hours:

As a follow-up to the initial report, within the following 48 hours of awareness of the event, the investigator shall provide further information, as applicable, on the unanticipated device event or the unanticipated problem in the form of a written narrative. This should include a copy of the completed Unanticipated Problem form, and any other diagnostic information that will assist the understanding of the event. Significant new information on ongoing unanticipated adverse device effects shall be provided promptly to the study sponsor.

Other Reportable events:

Deviations from the study protocol

Deviations from the protocol must receive both Sponsor and the investigator's IRB approval before they are initiated. Any protocol deviations initiated without Sponsor and the investigator's IRB approval that may affect the scientific soundness of the study, or affect the rights, safety, or welfare of study subjects, must be reported to the Sponsor and to the investigator's IRB as soon as a possible, but **no later than 5 working days** of the protocol deviation.

• Withdrawal of IRB approval

An investigator shall report to the sponsor a withdrawal of approval by the investigator's reviewing IRB as soon as a possible, but **no later than 5 working days** of the IRB notification of withdrawal of approval.

8.3.2 Investigator reporting: notifying the IRB

Federal regulations require timely reporting by investigators to their local IRB of unanticipated problems posing risks to subjects or others. The following describes the NYULMC IRB reporting requirements, though Investigators at participating sites are responsible for meeting the specific requirements of their IRB of record.

Report Promptly, but no later than 5 working days:

Researchers are required to submit reports of the following problems promptly but no later than 5 working days from the time the investigator becomes aware of the event:

Unanticipated problems including adverse events that are unexpected and related

- Unexpected: An event is "unexpected" when its specificity and severity are not accurately reflected in the protocol-related documents, such as the IRB-approved research protocol, any applicable investigator brochure, and the current IRB-approved informed consent document and other relevant sources of information, such as product labeling and package inserts.
- Related to the research procedures: An event is related to the research procedures if in the opinion of the principal investigator or sponsor, the event was more likely than not to be caused by the research procedures.
- Harmful: either caused harm to subjects or others, or placed them at increased risk

Other Reportable events:

The following events also require prompt reporting to the IRB, though no later than 5 working days:

- Complaint of a research subject when the complaint indicates unexpected risks or the complaint cannot be resolved by the research team.
- Protocol deviations or violations (includes intentional and accidental/unintentional deviations from the IRB approved protocol) for any of the following situations:
 - one or more participants were placed at increased risk of harm
 - the event has the potential to occur again
 - the deviation was necessary to protect a subject from immediate harm
- Breach of confidentiality
- Incarceration of a participant when the research was not previously approved under Subpart C and the investigator believes it is in the best interest of the subject to remain on the study.
- New Information indicating a change to the risks or potential benefits of the research, in terms of severity or frequency. (e.g. analysis indicates lower-than-expected response rate or a more severe or frequent side effect; Other research finds arm of study has no therapeutic value; FDA labeling change or withdrawal from market)

Reporting Process

The reportable events noted above will be reported to the IRB using the form: "Reportable Event Form" or as a written report of the event (including a description of the event with information regarding its fulfillment of the above criteria, follow-up/resolution and need for revision to consent form and/or other study documentation).

Copies of each report and documentation of IRB notification and receipt will be kept in the Clinical Investigator's study file.

8.3.3 Sponsor reporting: Notifying the FDA

The study sponsor is required to report certain study events in an expedited fashion to the FDA. These written notifications of adverse events are referred to as IND safety reports. The following describes the safety reporting requirements by timeline for reporting and associated type of event:

- Within 7 calendar days (via telephone or facsimile report)
 Any study event that is:
 - associated with the use of the study drug
 - unexpected.
 - fatal or life-threatening
- Within 15 calendar days (via written report)

Any study event that is:

- associated with the use of the study drug,
- unexpected, and
- serious, but not fatal or life-threatening

-or-

 a previous adverse event that was not initially deemed reportable but is later found to fit the criteria for reporting (reporting within 15 calendar days from when event was deemed reportable).

Any finding from tests in laboratory animals that:

 suggest a significant risk for human subjects including reports of mutagenicity, teratogenicity, or carcinogenicity.

Additional reporting requirements

Sponsors are also required to identify in IND safety reports all previous reports concerning similar adverse events and to analyze the significance of the current event in light of the previous reports.

Reporting Process

Adverse events may be submitted on FDA Form 3500A or in a narrative format. If supplied as in a narrative format, the minimum information to be supplied is noted above at the beginning of section 8.3. The contact information for submitting IND safety reports is noted below:

8.3.4 Sponsor reporting: Notifying participating investigators

It is the responsibility of the study sponsor to notify all participating investigators of any adverse event that meets the FDA 15-day reporting requirement criteria as note above in section 8.3.4. The same materials and timeline used to report to the FDA are used for notifying participating investigators.

8.4 Unblinding Procedures

Unblinging will be at the PIs discretion on a case by case basis.

8.5 Stopping Rules

There are no specific stopping rules.

The principal investigator ([name], MD) together with the treating investigators will be responsible for ensuring both data integrity and that patients who participate in the study will be properly cared for, and that all adverse events are noted, followed and reported to the IRB (when appropriate). In addition, a DSMB Chaired by [name] will oversee the protocols outlined in this proposal. Any adverse event rated moderate or severe will be immediately reported to the IRB and the DSMB. All adverse events will be reported to the IRB on an annual basis. All necessary information will be reported to the FDA in accordance with the guidelines outlined for a treatment IND.

8.6 Medical Monitoring

It is the responsibility of the Principal Investigator to oversee the safety of the study at his/her site. This safety monitoring will include careful assessment and appropriate reporting of adverse events as noted above, as well as the construction and implementation of a site data and safety-monitoring plan (see section 9 Auditing, Monitoring and Inspecting). Medical monitoring will include a regular assessment of the number and type of serious adverse events.

8.6.1 Data Monitoring Committee

Safety data will be collected at each study visit (12 lead ECG, urinalysis, CBC, metabolic panel, vitals, neurological & physical examinations). In addition, to further monitor safety between study visits, we will contact

by phone patients on the day of and again 7-days after adjusting doses to question them about potential adverse events. We will continue to call patients on a weekly basis during the outpatient phase to monitor adverse events (table 2). All data will be collected on standardized case report forms. Data will be entered into a study database created on the REDCap platform and hosted by NYU's Clinical and Translational Science Institute (CTSI). All data will be de-identified, encrypted and stored behind a secure firewall accessible only to designated investigators. To check for potential data entry errors, data will be graphed and examined for outlying values prior to analysis.

A data and safety monitoring board (DSMB, Chaired by [name]) will review safety data on an ongoing basis. The study will continue until the target number of patients is enrolled or the DSMB recommends stopping the trial. To allow for a flexible trial design, there will be an interim efficacy analysis with access to the un-blinded after the first 15 patients have completed the trial. If carbidopa is found to significantly reduce blood pressure variability and the 300 mg/day (low-dose) is found to be equivalently effective as the 600mg/day (high-dose), we will decide, with the DSMB, whether to amend the protocol to add an additional treatment arm to test doses lower than 300 mg/day. Alternatively, if there is insufficient evidence to suggest that 600 mg/day of carbidopa reduces blood pressure variability, before terminating the trial for futility, we will drop the ineffective arms and collect exploratory data to explore the effectiveness of higher carbidopa doses up to 900 mg/day (for 28 days). We will modify the trial to include a titration from upwards of 600 mg/day in increments of 50 mg/day increases per week. To monitor safety closely, we will collect additional safety bloods (CBC and metabolic panel), 12 lead ECG and conduct comprehensive neurological examinations with each incremental titration step up and patients will be contacted by interim phone-calls to monitor adverse events. Only patients that live within 2-hours of the Dysautonomia Center will be included in the subsection to explore the efficacy of higher carbidopa dosages. We will conduct new power analyzes with the accumulated data and revise the sample size accordingly. Final analysis will be performed after the final study patient has completed the trial and the study is closed for enrollment. All end-points will be first examined using descriptive statistics. Each patient will serve as their own control allowing paired comparisons to be made between high-dose, low-dose and placebo data.

9 Data Handling and Record Keeping

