4.3 Subject Recruitment and Screening

Since most patient with FD take medications by opening capsules or crushing pills and flushing them through their gastrostomy, it is necessary to use carbidopa powder (rather then re-encapsulate the commercially available pills) to maintain treatment allocation concealment. Subjects randomized to receive placebo will receive an identical small capsule containing a matching powder, as we've previously done. Thirty subjects will be randomized. Randomization will be performed by the Investigational Pharmacy of NYU, and participants, caregivers and assessors will be blinded at all times from the randomization sequence. Randomization sequences will be generated using computer-based system using a permuted block design and the Investigational Pharmacy of NYU will dispense all medications and provide dosing instructions for titration down and washout between treatment arms (Appendix). Investigators will not be involved in specifying the actual doses patients take and will remain blind to treatment allocation throughout. The PI will have the capacity to break the blind and remove any patient from the study at anytime for safety concerns. To monitor compliance, patients will be instructed to return all unused study medications at study visits.

4.3.1 Assessment of mental capacity to consent.

There are few formal assessments of cognitive function in patients with FD. Published studies likely underestimate the frequency of cognitive impairment owing to the bias of only "higher functioning" patients being able to complete the cognitive assessment tests. We estimate that around 40% of patients have impaired cognitive function. Given this we anticipate difficultly completing recruitment goals without enrolling patients with diminished capacity, as this is a rare genetic disease. We have included the following measures to ensure adequate assessment of cognitive impairment and capacity are in place.

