For in office visits, patients will be instructed to take their study pill 3-h before attending the office visit. The timing of the medication and testing will be noted in the case report forms. Patients will bring with them to the office visit a 24-hour urine collection for urine catecholamine assay. They will be instructed to arrive wearing the ambulatory BP monitor. Upon arrival at the clinic, vital signs will be taken and blood pressure will be measured supine, seated and standing. Ambulatory monitor blood pressure values will be calibrated against simultaneous measurements of blood pressure in the opposite arm using an automated sphygmomanometer during the orthostatic challenge. Ambulatory recordings will be downloaded and the data reviewed for quality. If recordings are found to be inadequate, they will be repeated with the patient remaining on the same dose of medication for 1 additional day before titrating down and washout. Patients will be instructed to return their unused medications to monitor compliance Beat-to-beat BP and RR interval changes before/during stoop and serial 7 subtractions will be repeated. Patients will have blood drawn and urine collected for safety measures and a 12-lead ECG will be performed. Neurological and physical exam will be performed. Patients will be dispensed and dosing instructions will be provided (Appendix).

[figure not shown]

Fig 8: Details of the telemedine visits: Study visits may be performed virtually, through 2-way audio visual conferencing. See text for details.

As shown in Figure 8, for telemedicine visits, prior to the visit, investigators will ensure patients have access to 2-way video conferencing with audio and that continuous HR measurements can be acquired from the wireless wrist tracker. Symptoms diaries will be collected. Patients will be instructed to continue their three times daily dosage of carbidopa. Safety labs, ambulatory blood pressure monitoring and 24-h urine collections will be performed while at the steady state.

Before the call, patients will be instructed to (1) weigh themselves in the morning, (2) to take their study medication 3-h before the scheduled time of the teleconference, (3) email a photograph of their unused pills for medication compliance check, (4) be wearing their ambulatory monitor at the time of the video call, and (5) have their wrist-based heart rate tracker on.

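### Section 8.6.1 lets the trial team act on unblinded interim efficacy results by dose and sets no limit on what that team sees, in tension with the blinding promised in 4.3

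*Combined protocol and SAP*

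**What the plan says.** Section 8.6.1 (Data Monitoring Committee) announces that "there will be an interim efficacy analysis with access to the un-blinded after the first 15 patients have completed the trial". Three actions may follow:

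- If carbidopa works and the low dose matches the high dose: "we will decide, with the DSMB, whether to amend the protocol to add an additional treatment arm to test doses lower than 300 mg/day".
- If the high dose shows too little effect: "we will drop the ineffective arms and collect exploratory data to explore the effectiveness of higher carbidopa doses". The DSMB is not named in this branch.
- On sample size: "We will conduct new power analyzes with the accumulated data and revise the sample size accordingly". The DSMB is not named here either.

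The DSMB's ongoing review is described in the same section as covering safety data. The study database is open to designated investigators.

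Section 4.3 (Subject Recruitment and Screening) says: "Investigators will not be involved in specifying the actual doses patients take and will remain blind to treatment allocation throughout". It also has participants, caregivers and assessors blinded to the randomization sequence at all times. The stated exceptions are the PI's safety code-break in 4.3 and section 8.4: "Unblinging will be at the PIs discretion on a case by case basis". Both concern individual patients. Neither provides for a planned efficacy look.

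Section 7.2 mentions a dedicated trial statistician but does not say whether that person is separate from trial conduct. No section describes a closed DSMB session, names who prepares the interim report, or says what the investigators are told.

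**The concern.** The point is who sees the interim results, not the thresholds for acting on them. The people who act on results by dose appear to be the people who run the rest of the trial. At a single centre they enrol patients, run the stand and stress tests, examine patients, question them on adverse events, judge relatedness and review the ambulatory recordings. Under 3.1, study medication may also be interrupted and resumed around intercurrent events.

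A team that knows at mid-trial which dose looks effective or poorly tolerated may change whom it enrols, how hard it probes for symptoms, or how it attributes events. Safety and tolerability is Aim 1, and much of it depends on such judgement. A difference between patients before and after the look would then be hard to interpret.

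**Working it through.** **1. The plan's own figures.** Section 7.2 targets 30 patients, assumes about 15% dropout and enrols 36. Check: 30 / (1 − 0.15) = 35.3, rounded up to 36, as stated. For n = 30, SD of the difference 4.4, alpha 0.05 and 80% power, a paired t-test has a detectable difference of 2.046 one-sided and 2.329 two-sided. This matches the 2.0 and 2.3 in Table 3, so 30 is the analysis target.

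**2. How much of the trial follows the look.** The look comes after 15 completers.

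- Against the target: 30 − 15 = 15 patients, or 15/30 = 50%.
- If 36 are enrolled with 15% dropout: 36 × 0.85 = 30.6 expected completers, and 30.6 − 15 = 15.6 after the look.
- If only 30 are randomized, as 4.3 says, with the same dropout: 30 × 0.85 = 25.5, and 25.5 − 15 = 10.5 after the look.

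So roughly 10 to 16 completers follow the look. At three on-treatment recordings each, 15 × 3 = 45 of 30 × 3 = 90 recordings is an upper bound against the target, because some patients will be part-way through at the look.

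**3. Who acts.** In 8.6.1 the word *we* is distinct from the DSMB, since it decides jointly with it. The same *we* telephones patients about adverse events, collects the additional safety bloods and performs the neurological examinations. The natural reading is the site team.

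**4. Sections 4.3 and 8.6.1 side by side.** Section 4.3 promises blindness to *allocation*. There are two cases:

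- *Only results pooled by dose are shown.* The team learns comparative efficacy but not any later patient's sequence, and the pharmacy keeps the codes (5.4, 5.8). Section 4.3 can be kept to the letter.
- *Patient-level data are opened.* The allocations of the first 15 completers become known, and 4.3 is broken for them. Sequences of patients still in the trial could also be partly predictable. Randomization is in permuted blocks over three sequences at 1:1:1, with block size not stated. If the block size were three (an assumption), knowing two members of a block would determine the third. Larger blocks reveal less.

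Section 8.6.1 does not say which case applies.

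**5. What is open to influence.**

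- *Less open:* both primary endpoints (3.2) come from an automated ambulatory monitor. Section 6 (Visit 2) says "If recordings are found to be inadequate, they will be repeated with the patient remaining on the same dose of medication for 1 additional day", and the ambulatory monitoring text makes that numeric: a success rate below 80%, or office and ambulatory readings differing by more than 20%. Cuff size and the 24-hour window are also held constant.
- *More open:* enrolment, physical and neurological examinations, adverse-event questioning and attribution, conduct of the stand and stress tests, and medication interruptions.

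**The case against.** The strongest reply is that access by investigators is inferred. The key sentence is incomplete and names nobody. A team can take part in an amendment decision on a DSMB recommendation alone. The *we* that redoes the power analysis could be the statistician of 7.2. This is fair, but the text makes the first decision joint, gives the other two to the team without naming the DSMB, and restricts nothing.

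A reader might infer that 4.3 and 8.6.1 cannot both be followed. The documents do not support that: with pooled results only, both can be. The firm statement is that the restriction which would make them compatible is missing.

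A reader might also infer that the second half is no longer double-blind or that the primary endpoints are compromised. That too goes beyond the text. Each patient is their own control over three periods, and knowing that a dose looks effective does not tell staff which period a patient is in. Without allocation knowledge, changed behaviour is not aimed at a particular treatment. The automated readings and numeric triggers narrow the scope further.

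Finally, a reader might count 21 of 36 patients and 63 of 108 recordings as falling after the look. Those figures treat the expected dropouts as finishers.

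**Conclusion.** The point holds as a gap in the plan. As written, 8.6.1 allows the single-centre team to learn comparative efficacy by dose at mid-trial, and possibly individual allocations, while 4.3 says investigators stay blind. It is a tension in any case, and a direct contradiction only if patient-level data are opened.

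The period affected covers up to about 15 of the 30 target patients. That count measures exposure, not bias; the documents give no basis for putting a size on the bias. The likely effect is on Aim 1 assessments, examinations and enrolment more than on the ambulatory primary endpoints.

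The conclusion assumes that *we* in 8.6.1 means the site team and that no separate DSMB charter restricts access; none is mentioned. It is a worthwhile, low-cost improvement and does not by itself invalidate the trial.

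**What to change.** Amend 8.6.1 to state that:

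- a statistician with no role in trial conduct prepares the unblinded interim report, for a DSMB closed session only;
- the data of the first 15 completers are cleaned and locked before codes are released to that statistician;
- the PI, treating investigators, coordinators and assessors receive only the DSMB's recommendation, with no results by treatment and no patient-level codes until database lock;
- any sample-size revision is calculated by that statistician and passed on through the DSMB;
- any change to the arms follows from the DSMB's recommendation.

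The DSMB's remit in 8.6.1 should be extended to the interim efficacy report. Section 4.3 should be reconciled with the new text, and the plan should say whether the statistician of 7.2 or a separate person fills the unblinded role and who performs the final analysis.

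The cost is protocol and DSMB wording, plus a second statistician if the one in 7.2 is involved in conduct. There are two drawbacks. Investigators cannot debate the interim numbers. And because 8.6.1 ties each modification to a particular finding, a recommendation to modify will still partly signal the result. The final report should therefore identify data collected before and after any modification.

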Benzodiazepines (like diazepam and clonazepam ¹¹) are effective anxiolytics and frequently lower blood pressure during a prolonged anxiety-induced paroxysmal hypertensive attack. Many patients, however, quickly become tolerant and require increasing doses, ^{7,13} which can cause severe respiratory depression as patient also lack inputs from chemoreceptors. ¹⁸ The central sympatholytic agent clonidine has been used with some success, ¹¹ but its use is limited by the unwanted side effects of sedation, hypotension and rebound hypertension. Beta-blockers and ACE-inhibitors frequently produce hypokalemia. Vasodilators like calcium channel blockers, hydralazine and nitrates frequently worsen orthostatic hypotension.

Dopa-Decarboxylase-Inhibition and Blood Pressure Variability:

At rest, carbidopa does not have profound effects on tissue concentrations of norepinephrine³³ or on blood pressure.³⁶ In patients with classic (efferent) autonomic failure, carbidopa does not worsen orthostatic hypotension.³⁷ Most relevant to this proposal, experimental data shows that at times of emotional arousal, when rates of catecholamines synthesis increase, carbidopa effectively blocks the additional production of dopamine, norepinephrine and epinephrine.³³ Animal data shows that the suppression of norepinephrine synthesis in sympathetic nerves is even more effective at larger doses.³⁸ If carbidopa had the same effect in patients with FD, inhibiting catecholamine surges at times of arousal would help dampen paroxysmal hypertensive peaks and should subsequently reduce overall variability. Since carbidopa itself cannot cross the blood brain barrier, ¹² even at high doses, ^{36,39} it has no effects on the CNS, thus making it a viable alternative to benzodiazepines and clonidine for the treatment of catecholamine-induced paroxysmal hypertension in FD. Its effects on the severity of orthostatic hypotension in patients with FD are not clear and warrant further investigation to ensure the drug is safe.¹³

C: Preliminary Data

Recently, in a double-bind, placebo-controlled trial sponsored by the FDA's Office of Orphan Products Development ¹³ we showed the short-term safety of carbidopa and its antiemetic efficacy in patients with FD. Carbidopa successfully lessened the nausea/retching/vomiting episodes and reduced the need for benzodiazepines.¹³ Preliminary results show carbidopa also has a beneficial effect on stabilizing the blood pressure and reducing its variability.

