1.6.3 Potential benefits

No benefits can be guaranteed nor will they be implied when consent is obtained. Under the conditions of careful bedside monitoring outlined in this proposal, the risk to any subject will be minimized. We consider these risks smaller than the practical and theoretical benefits derived from the information obtained.

There is a potential benefit that carbidopa may reduce blood pressure variability and paroxysmal

hypertension.

2 Study Objectives

Aim 1: To evaluate the safety and tolerability of carbidopa in FD patients with particular emphasis on the orthostatic fall in blood pressure.

Aim 2: As proof of concept, examine the hemodynamic effects of carbidopa and determine its effects on norepinephrine production, BP variability and paroxysmal hypertension.

Aim 3: In a dose finding study, compare the effects of low (300 mg/day) and high (600 mg/day) dose carbidopa blockade vs. placebo on BP variability and paroxysmal hypertension.

3 Study Design

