5.7 Packaging

Study drug will be packaged in 100 mg/ 200mg/ and matching placebo capsules and dispensed in a 30 day supply.

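### The branch above 600 mg/day opens on lack of efficacy with no stated safety review, and its step-up monitoring names no orthostatic assessment

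*Combined protocol and SAP*

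**What the plan says.** Section 8.6.1 plans one unblinded look: "there will be an interim efficacy analysis with access to the un-blinded after the first 15 patients have completed the trial". Two branches can follow.

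- **Downward.** If carbidopa works and the two doses look equally effective, the investigators decide jointly with the DSMB whether to amend the protocol and test doses below 300 mg/day.
- **Upward.** This branch opens "if there is insufficient evidence to suggest that 600 mg/day of carbidopa reduces blood pressure variability". The ineffective arms are then dropped and exploratory data are collected to "explore the effectiveness of higher carbidopa doses up to 900 mg/day (for 28 days". The dose rises from 600 mg/day by 50 mg/day each week. No joint decision with the DSMB is written for this branch.

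For the upward branch the safety text reads "we will collect additional safety bloods (CBC and metabolic panel), 12 lead ECG and conduct comprehensive neurological examinations with each incremental titration step up", with interim phone calls about adverse events.

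Elsewhere, Aim 1 in Section 2 is "To evaluate the safety and tolerability of carbidopa in FD patients with particular emphasis on the orthostatic fall in blood pressure". Section 1.4 says of carbidopa: "Its effects on the severity of orthostatic hypotension in patients with FD are not clear and warrant further investigation". Section 3.4 lists the active stand test, OH-Q worsening and lowest 24-h systolic BP as tolerability measures. Section 8.5 states: "There are no specific stopping rules".

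**The concern.** The upward branch goes beyond the trial's own dose range and beyond the FD ambulatory BP data in Section 1.4, which cover 450 to 600 mg/day. Two things are missing from its description.

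First, the only stated condition for opening it concerns efficacy. The interim is described as an efficacy analysis, and nothing says that the unblinded orthostatic and adverse event results on 600 mg/day are examined before doses rise. By then those data exist: each of the 15 completers will have been scheduled for a stand test and an OH-Q at the end of the 600 mg/day, 300 mg/day and placebo periods.

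Second, the step-up list omits the one risk that Aim 1 singles out. If staff follow the list as written, the branch yields laboratory, ECG and neurological data at each dose level but no standing BP by dose level. It could then say little about orthostatic tolerability at the doses it is meant to explore.

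The dose, step rate and duration also need to be read together, because the stated 28 days do not match the weekly steps on every reading.

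**Working it through.** The plan gives no figure of its own on this point to reproduce. The check is a comparison of schedules followed by step arithmetic.

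**1. Schedules side by side** (Table 1 and Section 6 against the step-up text in Section 8.6.1)

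| Assessment | Main trial | Upward branch, each step |
|---|---|---|
| Supine/seated/standing BP | study visits, 28 days apart | not named |
| OH-Q | study visits | not named |
| 24-h ambulatory BP (gives lowest 24-h systolic BP) | study visits | not named |
| CBC, metabolic panel | study visits | named |
| 12-lead ECG | study visits | named |
| Neurological examination | study visits | named |
| Adverse event phone calls | day of dose change, day 7, then weekly | interim calls, timing not given |

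All three measures that bear on low blood pressure are absent from the right-hand column. Section 8.6.1 also collects vitals at each study visit, but this does not settle the matter. Section 3.4 places sitting and standing BP among the safety measures, while Table 1 defines vital signs as temperature and weight and gives postural BP a separate row.

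**2. Spacing of standing BP if the 28-day visits continue** (assumed; the plan does not say)

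Dose steps between visits: 28 / 7 = 4.

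For example, take the first step as day 0 and visits on days 28 and 56, each before any step due that day. The steps to 650, 700, 750 and 800 mg/day fall on days 0, 7, 14 and 21, so the day-28 visit measures 800. The steps to 850 and 900 fall on days 28 and 35, so the day-56 visit measures 900. On this alignment, four of the six dose levels (650, 700, 750 and 850) have no standing measurement.

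**3. Time needed to reach 900 mg/day**

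- Steps: (900 − 600) / 50 = 6.
- First step on day 0: the sixth falls on day (6 − 1) × 7 = 35.
- One week at 600 mg/day first: the sixth falls on day 6 × 7 = 42.

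**4. What the 28 days could mean**

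- *Total length of the branch.* Four weekly dose levels fit. The highest is 600 + 4 × 50 = 800 mg/day, or 600 + 3 × 50 = 750 mg/day if the first week is at 600. Neither reaches 900.
- *Time at 900 mg/day.* Five weeks at 650 to 850 plus four at 900 make 5 + 4 = 9 weeks, or 63 days, above 600 mg/day. The branch lasts 63 days, or 63 + 7 = 70 days with an initial week at 600.

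Only the second reading is compatible with the stated maximum.

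**The case against.** The strongest reply is that the step-up items are called *additional*, which suggests they are added to the ordinary visits. If so, standing BP is still taken every 28 days, and laboratory tests, ECG and neurological examination are done more often than before. The main trial itself takes no standing BP at a dose change, only phone calls. A reader might infer that the highest doses get less orthostatic surveillance than the main trial; the documents do not support that, because nothing says the Table 1 visits stop. What remains is that nothing says they continue either, and even if they do, several dose steps can fall between measurements.

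Second, efficacy is not the only control in the background. The DSMB reviews safety on an ongoing basis and can recommend stopping. Section 8.5 sends every moderate or severe adverse event to the DSMB and IRB at once, and Section 11 sends amendments to the IRB. The branch may fairly be read as an outline to be completed by amendment. This tempers the point about the trigger. It does not supply a by-treatment review of the 600 mg/day data linked to opening the branch, and the contrast with the downward branch, where a joint DSMB decision is written, remains.

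Third, it would be too strong to say that a worsening orthostatic fall could be found only by phone, or that the branch gives no Aim 1 data. The step-up tests are themselves safety data, caregivers are asked to record adverse events, and a branch that explores BP variability presumably uses ambulatory recordings, which give the lowest systolic BP. The plan does not say when those recordings would be made.

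**Conclusion.** The point holds as a gap and an inconsistency within the plan. Section 8.6.1 opens escalation above 600 mg/day on an efficacy finding with no stated safety review tied to that step. Its step-up list names none of the orthostatic measures that Aim 1, Section 3.4 and Table 1 rely on, and it leaves open whether the Table 1 assessments carry over. If they do, up to four weekly steps can pass between standing measurements; if they do not, none is specified over as many as six steps.

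The 28-day figure is ambiguous. It cannot include the titration, since 900 mg/day is reached on day 35 at the earliest. Read as time at 900 mg/day, it gives about 9 weeks above 600 mg/day. These results assume that every step is 50 mg/day, lasts one week, and that no step is skipped or held.

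Two further inferences should not be drawn. Ten weeks is the longer possible length of the branch, but it counts a week at 600 mg/day and so is not time above that dose. Nor do the capsule strengths in Section 5.7 ("Study drug will be packaged in 100 mg/ 200mg/ and matching placebo capsules") show that some steps cannot be made: they describe supply for the main-trial doses, and the product is prepared from powder (Section 4.3) by a compounding pharmacy (Section 5.9.1).

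The sponsor should correct this before the interim. It does not affect the main comparison of the two doses with placebo.

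**What to change.** All changes are to the wording of Section 8.6.1.

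1. Reconcile the step-up list with Aim 1, Section 3.4 and Table 1 by adding the existing supine/seated/standing BP test and the OH-Q to the assessments at each step, and state whether the other Table 1 assessments continue. The timed test takes 5 + 2 + 5 = 12 minutes (Section 1.5, Fig. 6 legend), at most 6 × 12 = 72 minutes per patient over six steps, at visits already needed for an ECG and neurological examination. The 10-item OH-Q adds a little more.
2. Include in the unblinded interim seen by the DSMB, by treatment, the active-stand fall, lowest 24-h systolic BP, OH-Q and adverse events, and state what safety review precedes escalation. The cost is one set of tables from data the main trial already collects.
3. State what the 28 days cover, and reconcile that with the weekly step rate and the 900 mg/day maximum.

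No dose, step size or escalation criterion is proposed here; these are for the sponsor and DSMB to decide.
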